8.1.4. Assessments Below and Above the Limit of Quantification

For summarization of PK concentration values and data analysis, assessments that are below the lower limit of quantification (LLOQ) will be set to zero prior to summarization. For PK concentration graphs, assessments that are below the lower limit of quantification will be set to half of LLOQ prior to graphing. For PK concentration assessments that are above the upper limit of quantification (ULOQ), the record will be set to missing prior to summarization or graphing. For other exploratory PK analysis such as population PK, assessment that are below the LLOQ may be defined differently.

For all other assessments that are below the lower limit of quantification will be imputed to half of the LLOQ for summarization; assessments that are above the upper limit of quantification will be imputed to the ULOQ for summarization.

For listings, records that are LLOQ or ULOQ will be listed as such together with the imputed value in separate columns.

8.2. Pharmacokinetic Analyses

Trough serum concentration will be summarized using the PK Analysis Set.

The trough serum concentration of BIO89-100 over time will be listed and plotted by individual subject and also summarized by nominal study visit. Serum concentration data will also be presented using descriptive statistics. Mean and individual serum concentration vs. time plots will be produced on both the linear/linear scale and on the semi-logarithmic scale.

8.3. Study Subjects

Subject enrollment by site will be summarized. The number of subjects who were screened, enrolled, early discontinued from IP, early discontinued from study, and completers will be summarized.

8.3.1. Subject Disposition

Subject disposition will be presented for the Full Analysis Set. The number of subjects enrolled, included in each analysis set, who completed study or had early terminated from the study and the reason, who completed IP regimen or discontinued IP regimen prematurely and the reason will be summarized. The number of subjects who were screened will be summarized.

In addition, a listing will be provided for subjects who had been impacted by COVID-19, e.g., study interruptions and the duration of their study interruption, withdrew from IP, withdrew from study, or had protocol deviation.

8.3.2. Demographics and Baseline Characteristics

Demographics and baseline characteristics data will be summarized descriptively using Full Analysis Set. Demographics and baseline characteristics include but not limited to, age (continuous and categories: <65, 65 to <75 years), sex, race and ethnicity, height, body weight, body mass index (continuous and categories: 25 to <30, 30 to <35, and $\geq 35 \text{ kg/m}^2$), [REDACTED], central obesity (waist circumference of >102 cm for males, >88 cm for females, or body mass index (BMI) $>30 \text{ kg/m}^2$); [REDACTED], triglycerides (continuous and categories: <150, 150 to <200 and $\geq 200 \text{ mg/dL}$), non-HDL, HDL-c, LDL-c (continuous and categories: <130, $\geq 130 \text{ mg/dL}$), [REDACTED], ALT, increased ALT (ALT $\geq 40 \text{ U/L}$ in males, ALT $\geq 30 \text{ U/L}$ in females), AST, adiponectin, Pro-C3, Pro-C3 subgroup ($<14.71, \geq 14.71 \text{ ng/mL}$), [REDACTED]; MRI-PDFF, endogenous FGF21, T2D history (yes/no), HbA1c, fasting plasma glucose.

8.3.3. Baseline Biopsy

The number and percentage of subjects with biopsies within 24 weeks of baseline including qualified historical biopsy and on-study biopsy during screening will be summarized by fibrosis stage (F2, F3), NAS (continuous with range, categorical: score from 0 to 8), steatosis score (continuous with range, categorical), ballooning degeneration score (quartiles, categorical), lobular inflammation score (continuous with range, categorical) for the Full Analysis Set. The percentages for this table will be based on the number of subjects with biopsies within 24 weeks in the Full Analysis Set.

8.3.4. Medical History

The number and percentage of subjects will be summarized by medical history code with system organ class (SOC) and preferred term (PT) for the Full Analysis Set. Medical history will be coded by Medical Dictionary for Regulatory Activities (MedDRA version 23.1 – Sep 2020).

8.3.5. Inclusion/Exclusion Criteria

Inclusion and exclusion criteria failures will not be summarized, but will be listed for the Full Analysis Set.

8.3.6. Investigational Product Administration

IP administration data such as the number and percentage of subjects who were administered full doses of IP each time, the number and percentage of subjects who were administered at least one partial dose, total number of injections administered over the study, IP exposure, relative dose intensity and IP compliance over the entire study will be summarized for the Full Analysis Set.

All IP administration data including injection site, volume of incomplete injections -and reason for incompleteness, full or partial doses administered and total volume of injections will be listed by visit.

Relative dose intensity is the ratio of actual dose intensity (mg) to planned dose intensity (mg). Actual dose intensity (mg) is equal to the cumulative actual dose (mg) divided by 20. Dose compliance percentage is defined as the actual number of received doses divided by the expected number of doses to be received up to EOS. Partial doses contribute to the actual number of received doses.

8.3.7. Concomitant Medication

The World Health Organization Drug Dictionary (B3 WHO Drug Global – Mar 2019) will be used to code the verbatim descriptions of prior and concomitant medications into the Anatomic Therapeutic Chemistry (ATC) classification system. Each verbatim name will be classified by anatomical main group, ATC level 1, therapeutic subgroup, ATC level 2, pharmacological subgroup, ATC level 3, and chemical subgroup, ATC level 4.

The number and percentage of subjects receiving concomitant medications will be summarized by ATC classification level 2 and level 4 for the Full Analysis set.

Pre-treatment medications will not be summarized, but will be in listings.

Baseline medications will also be summarized by ATC classification level 2 and 4.

8.3.8. Concomitant Procedures

All procedures, pre-treatment and concomitant, will be listed.

8.3.9. Protocol Deviations

Protocol deviations will be summarized for the Full Analysis Set. All protocol deviations will be reviewed by study team to identify major deviations prior to database lock. Major protocol deviations will be flagged and summarized as well. All protocol deviations will be listed.

8.4. Pharmacodynamic Analyses

PD analysis will use Full Analysis Set, MRI Analysis Set, and Histology Biopsy Analysis Set.

8.4.1. Analysis of Histology

8.4.1.1. Histology Measurements from Central Reader

Endpoints of different histological responses will be summarized with the point estimates and 95% CIs of the proportions of subjects who meet the response criteria (defined in Sections 4.1.2, 4.2, and 4.4) at Day 141 using the Histology Biopsy Analysis Set.

Baseline, change from baseline in individual score including NASH CRN fibrosis score, ISHAK fibrosis score, NAS score, steatosis grade, lobular inflammation grade, and ballooning grade will be summarized using the Histology Biopsy Analysis Set and by subgroups. The proportions of

subjects who met ≥ 1 -point improvement in steatosis, ≥ 1 -point improvement in ballooning, ≥ 1 -point improvement in inflammation will be summarized in tables and plotted in bar charts.

Shift of fibrosis stage from baseline to Day 141 in CRN and ISHAK fibrosis scores will be summarized. Shift of individual NAS components from baseline to Day 141 will be summarized.

Bar charts of CRN and ISHAK fibrosis scores with baseline and Day 141 side by side may be presented.

A series of five horizontal black bars of varying lengths, decreasing from left to right, set against a white background. The bars are positioned in a staggered, non-linear fashion, creating a sense of depth or a visual timeline. The first bar is the shortest, followed by a longer one, then a very long one, then another long one, and finally a very short one on the far right.

8.4.2. Analyses of Anthropometric Measurements

The observed values and the change from baseline and percent change from baseline for body weight, BMI, [REDACTED] will be presented by visit.

MMRM analysis will be performed on weight. Line plots (\pm SE) of the change from baseline mean over time may be presented.

8.4.3. Analyses of Laboratory Parameters

8.4.3.1. Lipids

The observed values and the change from baseline and percent change from baseline for triglycerides, non-HDL cholesterol, HDL-c, LDL-c, [REDACTED] will be presented by visit.

MMRM analysis will be performed on all lipids parameters. Only records where fasting is confirmed will be used for summary and analysis.

The following categories will be included in the descriptive summary by visit:

- Triglycerides <150, 150 - <200, and ≥ 200 mg/dL
- LDL-c <130 and ≥ 130 mg/dL

Additional shift tables for lipids based on the following cut points will be provided for baseline versus post-baseline values, by visit:

- Triglycerides <150, 150 - <200, and ≥ 200 mg/dL
- Triglycerides <150, ≥ 150 mg/dL
- LDL-c <130 and ≥ 130 mg/dL
- LDL-c <100 and ≥ 100 mg/dL
- HDL-c <40 and ≥ 40 mg/dL for males, and <50 and ≥ 50 mg/dL for females

Line plots (\pm SE) of the change from baseline mean over time may be presented.

In addition, waterfall plots for the individual percent change from baseline to Day 85, change from baseline to Day 85, percent change from baseline to Day 113, change from baseline to Day 113 will be generated.

8.4.3.2. Liver Biomarkers

The observed values and the change from baseline for ALT, AST, Pro-C3, and [REDACTED] will be presented by visit. MMRM analysis will be performed on all four endpoints.

A listing of only abnormal liver biomarker records will be provided.

Line plots (\pm SE) of the change from baseline mean over time may be presented.

8.4.3.3. Suspected Drug Induced Liver Injury

Suspected drug induced liver injury will be summarized in two ways.

For subjects with baseline ALT or AST are within normal range, then the proportion of subjects meeting the following criteria will be summarized by visit and over the entire study; for entire study summary all visits including unscheduled will be considered and the maximum value will be selected among all visits:

- ALT or AST >2x ULN
- ALT or AST >8x ULN
- ALT or AST >5x ULN for a duration of at least 2 weeks
- ALT or AST >3x ULN and (total bilirubin (TB) >2x ULN or international normalized ratio (INR) >1.5)

- ALT or AST $>3x$ ULN (the protocol includes with the criteria the following that will not be considered in the summary table: with the appearance of fatigue, nausea, vomiting, right upper quadrant pain or tenderness, fever, rash, and/or eosinophilia [$>5\%$])

For subjects with baseline ALT or AST $>$ ULN, then the proportion of subjects meeting the following criteria will be summarized:

- ALT or AST $>2x$ ULN or bilirubin $>1.5x$ ULN
- Baseline ALT or AST $<2x$ ULN
 - ALT or AST $>5x$ baseline value
- Baseline ALT or AST $\geq 2x$ ULN but $<5x$ ULN
 - ALT or AST $>3x$ baseline value
- Baseline ALT or AST $\geq 5x$ ULN
 - ALT or AST $>2x$ baseline value
- ALT or AST increase $>2x$ baseline value AND the increase is accompanied by a concomitant total bilirubin increase to $>2x$ ULN OR the INR concomitantly increases by >0.2 .
- ALT or AST increase $>2x$ baseline value (the protocol includes with the criteria the following that will not be considered in the summary table: in the presence of signs and symptom(s) such as fatigue, nausea, vomiting, right upper quadrant pain or tenderness, fever, rash, and/or eosinophilia [$>5\%$])

An evaluation of drug induced serious hepatotoxicity (eDISH) plot will be generated. If there are subjects with Hy's law then these subjects' data will be listed.

Any subjects that meet the criteria for suspected drug-induced liver injury (DILI) will be summarized in a listing.

8.5. Safety Analyses

Safety analysis will use the Full Analysis Set.

8.5.1. Adverse Events

All adverse events will be coded using the MedDRA (version 23.1 – Sep 2020).

The incidence and number of events of the following will be summarized:

- Overall TEAE Summary*
- TEAEs by System Organ Class (SOC) and Preferred Term (PT)
- Serious TEAEs by SOC and PT
- Serious Related TEAEs by SOC and PT
- Serious TEAEs Leading to Study Discontinuation by SOC and PT
- Serious TEAEs Leading to IP Discontinuation by SOC and PT
- Related TEAEs by SOC and PT
- TEAEs Leading to Study Discontinuation by SOC and PT
- Fatal TEAE (will be provided in a listing)
- TEAEs by SOC, PT and Maximum CTCAE Grade
- TEAEs by SOC, PT and CTCAE Grade
- TEAEs Leading to IP Discontinuation by SOC and PT
- TEAEs by PT in Descending Frequency

When calculating incidence; subjects will only be counted once per SOC, PT, or grade.

When deriving relationship of AEs to study treatment, categories with the relationship of “definitely related”, “probably related”, and “possibly related” will be considered “related”. If an AE has missing relationship, it will be assumed to be related to the IP for analysis purposes. If an AE has missing CTCAE grade, the missing grade will not be imputed. A separate category for “missing” will be included in the table. Any TEAE related to COVID19 will be provided in a listing.

*In the Overall TEAE summary, the most severe CTCAE grade will be summarized for each subject.

8.5.2. Clinical Laboratory Evaluations

The observed values and the change from baseline for labs (biochemistry, hematology, and urinalysis) will be summarized by visit. Pharmacodynamic endpoints summarized via descriptive efficacy summaries will not be presented in the safety lab change from baseline tables.

MMRM analysis will be performed on HbA1c and adiponectin.

A listing of only abnormal labs (biochemistry, hematology, and urinalysis) will be provided.

Shift tables will use the reference range result of low, normal, high to summarize lab (biochemistry and hematology) or normal and abnormal for select urinalysis shifts from baseline to each post-baseline visit. All labs with a reference range result will be included in shift tables. The percentage of the shifts will be derived using the number of subjects at the baseline range level as the denominator. The normal and abnormal reference range is included in Appendix 12.3 in the appendix section.

8.5.3. Physical Examination Findings

Physical examination findings will be listed.

8.5.4. Vital Signs

The observed values and the change from baseline for vital signs will be summarized by visit.

The number of subjects meeting the following criteria will be summarized considering all post-baseline visits including unscheduled:

- Absolute value of SBP <90 mm Hg
- Absolute value of DBP <50 mm Hg
- Pulse rate <50 bpm
- Pulse rate >120 bpm
- Maximum increase from baseline in SBP \geq 30 mm Hg
- Maximum increase from baseline in DBP \geq 20 mm Hg
- Maximum decrease from baseline in SBP \geq 30 mm Hg
- Maximum decrease from baseline in DBP \geq 20 mm Hg

Shift tables will be used to summarize clinically significant shifts from baseline to each post baseline visit in the following criteria:

- SBP and DBP:

| Blood Pressure Category | Systolic mm Hg | | Diastolic mm Hg |
|-------------------------|----------------|--------|-----------------|
| Hypotension | <90 | Or | <60 |
| Normal | <120 | And | <80 |
| Elevated | 120-129 | And | <80 |
| Hypertension Stage 1 | 130-139 | Or | 80-89 |
| Hypertension Stage 2 | \geq 140 | Or | \geq 90 |
| Crisis | >180 | And/or | >120 |

- HR (bpm): <50; 50-89; 90-99, \geq 100

For the assignment of blood pressure category, since they are not mutually exclusive, the assignment priority is as follows: Crisis, Hypertension Stage 2, Hypertension Stage 1, Elevated, Normal and then Hypotension.

8.5.5. 12-Lead Electrocardiograms

The observed values and the change from baseline for 12-lead ECGs parameters will be summarized by visit. Only visits where ECGs were taken pre-dose will be summarized.

For corrected QT interval by Fridericia (QTcF), the number and percentage of subjects that have a change from baseline in QTcF >30 to 60 msec and >60 msec over the entire study considering all visits including unscheduled will be summarized.

Overall interpretation (Normal, Abnormal Not Clinically Significant and Abnormal Clinically Significant) will also be summarized.

The eCRF and central reader data will be listed in addition to a variable identifying if there is agreement between the PI and central reader (Y/N).

A shift table will be used to present the shifts from baseline to each post-baseline visit using the following criteria:

- QTcF <450 msec
- QTcF 450-480 msec
- QTcF 481-500 msec
- QTcF >500 msec
- Not Done/Missing

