4.3. Other Safety Endpoints

The other safety endpoints are:

- Subject incidence of TEAEs by severity
- Number of subjects who discontinued due to TEAEs
- Number of subjects who discontinued due to related TEAEs
- Change from baseline in vital signs
- Incidence and shifts of clinically significant vital signs
- Incidence of clinically significant physical examination findings
- Incidence and shifts of clinically significant electrocardiograms (ECG)
- Incidence and shifts of clinically significant laboratory abnormalities
- Change from baseline in safety laboratory evaluations including complete blood count (CBC), blood biochemistry, urinalysis and bone biomarkers (CTX and P1NP)

Immunogenicity measures:

- Incidence and characteristics of anti-drug antibodies (ADA) after dosing (e.g., titer and/or binding specificity, to the fibroblast growth factor 21 (FGF21) and polyethylene glycol (PEG) part of BIO89-100 and neutralizing immunogenicity)
- Impact/correlation of the presence of ADAs on serum BIO89-100 concentrations and clinical safety

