5.3.3. Study Baseline for Vital Signs

For vital signs of blood pressure and pulse, measurements will be taken in duplicate starting from enrollment. Baseline for these measures should be the average of all individual assessments during screening up to Study Day 1 and prior to first dose if subject is dosed.

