8.1.1. Statistical Notation and Presentation

All data collected from all subjects in the electronic data capture will be presented in the subject level listings. All continuous data will be listed with the same precision as presented in the

database. Data listings will be sorted by subject ID and time point. Missing values will be represented by an empty cell and no imputation will be made. If imputation is used for analysis, excluding treatment-emergent and concomitant medication determinations, the imputed values will be listed with a derivation type column in the listing indicating that origin of the imputed value.

Continuous data will be summarized in tables using number of subjects or sample size (n), mean, median, standard deviation (SD), minimum and maximum.

Categorical data will be summarized in two ways, by subject and by time point. Subject data will be summarized using the count of distinct subjects that fall in the category and the percentage of the total number of subjects. Population counts, either the number of subjects or the number of assessments at the time point, will be used as the denominator in the calculation of percentages unless specified otherwise.

The original units (conventional) and SI units will be presented in listings. In general, conventional units will be used for tables and figures, unless otherwise specified. Insulin will use the conventional unit of uU/mL; estimated glomerular filtration rate will be presented using SI units.

Minimum and maximum values will use the precisions of the original value. Means, least-squares (LS) means, and medians will be rounded to one decimal place greater than the precision of the original value up to a max of two decimal places. The limits of confidence intervals (CI), standard deviations (SD), and standard errors (SE) will be rounded to two decimal places greater than the precision of the original value. Derived PK and PD data (e.g., unit conversion) will be presented with three decimal places. Percentages will be rounded to the nearest tenth. Two-sided p-values will be presented with four decimal places and values less than 0.0001 will be presented as <.0001.

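### Part 2 blood-pressure shift table: Normal is assigned before Hypotension, so no whole-number reading can be classed as Hypotension

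*SAP*

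**What the plan says.** Section 8.5.4 of the Part 2 SAP plans a shift table from baseline to each post-baseline visit. Two of its category rows overlap: "Hypotension | <90 | Or | <60" and "Normal | <120 | And | <80". The other rows are Elevated (SBP 120-129 and DBP <80), Stage 1 (SBP 130-139 or DBP 80-89), Stage 2 (SBP ≥140 or DBP ≥90) and Crisis (SBP >180 and/or DBP >120). The section acknowledges that the categories overlap and states that "the assignment priority is as follows: Crisis, Hypertension Stage 2, Hypertension Stage 1, Elevated, Normal and then Hypotension".

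The same section counts subjects who cross fixed limits at any post-baseline visit: SBP <90, "Absolute value of DBP <50 mm Hg", and falls from baseline of at least 30 mmHg in SBP or 20 mmHg in DBP ("Maximum decrease from baseline in DBP").

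The table serves an endpoint in section 4.3, "Incidence and shifts of clinically significant vital signs". Section 5.3.3 makes the baseline a mean: "Baseline for these measures should be the average of all individual assessments during screening", continuing up to the first dose.

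**The concern.** The Normal row has no lower limit, so it contains every reading with SBP <120 and DBP <80 that meets the Hypotension definition. Ranking Normal first sends all of them to Normal. Every other whole-number reading is taken by Elevated or a hypertensive category before Hypotension is tested.

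Two misreadings follow. First, the Hypotension row is empty by construction, and a reader of the study report would take that as an observation. Second, a harmful change can look like an improvement: a subject who goes from 135/85 to 85/50 appears as Stage 1 to Normal. Part 2 has one open-label arm and no placebo, so its safety reading rests on descriptive tables such as this one.

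A smaller fault lies in the same table. The bands are written in whole numbers, while the Part 2 baseline is an average. A value such as 129.5/70 belongs to no category.

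**Working it through.** The plan gives no figure to reproduce. The check applies its own rule to all possible readings.

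**1. Can a whole-number reading reach Hypotension?** Take the category tests in the stated order.

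- SBP <120: DBP <80 gives Normal, DBP 80-89 Stage 1, DBP ≥90 Stage 2 or Crisis.
- SBP 120-129: DBP <80 gives Elevated, DBP 80-89 Stage 1, DBP ≥90 Stage 2 or Crisis.
- SBP 130-139: Stage 1 or higher, whatever the DBP.
- SBP ≥140: Stage 2 or Crisis.

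These cases cover every whole-number pair, and none reaches Hypotension.

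| Reading | Categories met | Assigned |
|---|---|---|
| 80/50 | Normal, Hypotension | Normal |
| 100/55 | Normal, Hypotension | Normal |
| 125/55 | Elevated, Hypotension | Elevated |
| 135/55 | Stage 1, Hypotension | Stage 1 |
| 129.5/55 | Hypotension only | Hypotension |
| 129.5/70 | none | unclassified |

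**2. How many pairs are misclassed as Normal?** Grid (an assumed plausible range): SBP 70-200, DBP 40-120, DBP below SBP, whole mmHg. Count pairs with SBP <120, DBP <80, and SBP <90 or DBP <60.

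- SBP 70-79: 30 + 31 + … + 39 = 345.
- SBP 80-89: 10 × 40 = 400.
- SBP 90-119 with DBP 40-59: 30 × 20 = 600.
- Total 345 + 400 + 600 = 1,345, all assigned Normal. Pairs assigned Hypotension: 0.

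**3. Which of these escape the separate absolute counts?** Those with SBP not below 90 and DBP not below 50: SBP 90-119 and DBP 50-59, or 30 × 10 = 300 pairs. All 300 are Normal under the stated order. With Hypotension ahead of Normal, all 300 become Hypotension.

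The fall counts catch such a reading only from a high enough baseline:

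- DBP fall ≥20: a reading of 50 needs baseline DBP ≥70, a reading of 55 needs ≥75, a reading of 59 needs ≥79.
- SBP fall ≥30: a reading of 90 needs baseline SBP ≥120, a reading of 119 needs ≥149.

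Example: baseline 115/65, later 105/55. Both pressures fall by 10, no count is triggered, and the shift table shows Normal to Normal.

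**4. Averaged values.** Same limits, 0.5 mmHg steps, no rounding before classification.

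- Assigned Hypotension: SBP 129.5 or 139.5 with DBP 40 to 59.5, or 2 × 40 = 80 pairs. These are not the low systolic pressures one expects in that row.
- Unclassified: SBP 129.5 or 139.5 with DBP 60 to 79.5 (2 × 40 = 80), plus DBP 89.5 with SBP 90 to 129.5 (80) or 139.5 (1). Total 80 + 81 = 161 pairs.
- With Hypotension ranked ahead of Elevated and Normal, and continuous bands: 0 unclassified. For example, 129.5/70 becomes Elevated.

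**The case against.** The best counter-argument concerns weight. The table is a secondary display in a cohort of about 20 subjects, and no primary or secondary endpoint or decision rule uses it. The same section counts SBP <90, DBP <50 and large falls, including at unscheduled visits. Section 8.1.1 adds that "All data collected from all subjects in the electronic data capture will be presented in the subject level listings". Vital-sign results that the investigator judges clinically significant also meet the adverse event definition in protocol section 9.3.1 and would appear in the adverse event tables. All of this stands, and it limits the harm to the table itself.

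The 50-59 diastolic range can also be questioned. The low limits in Part 2 exclusion criterion 24 are SBP <90 and DBP <50, and only this table calls DBP <60 low. That is fair, but the table is the sponsor's own definition and is introduced as showing clinically significant shifts. DBP 50-59 with SBP ≥120 likewise meets no absolute count; those readings go to Elevated or a hypertensive category rather than Normal.

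The figures for averaged values depend on the grid and on the absence of rounding, and the SAP does not say whether averages are rounded first. That also stands. The ordering fault does not depend on it.

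Finally, moving Hypotension a single place, ahead of Normal only, would cure the misclassification as Normal. Ranking it ahead of Elevated as well is a choice, not a necessity.

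**Conclusion.** The fault is in the rule as written. Under the stated order no whole-number reading can be classed as Hypotension, and every reading that meets the SAP's own hypotension definition with SBP <120 and DBP <80 is tabulated as Normal. This follows from the definitions and the order alone.

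The effect is confined to one descriptive safety table. The part not covered by an absolute count and shown as Normal is SBP 90-119 with DBP 50-59 (300 of 300 whole-number pairs), caught elsewhere only when the fall from baseline is large enough. The pair counts test the rule; the documents hold no data from which to estimate how many subjects would be affected. The secondary point, that averaged values can fall between bands, assumes averages are not rounded before classification. The table should be corrected, but the primary analyses are not at risk.

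**What to change.** In section 8.5.4 of the Part 2 SAP:

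- Rank Hypotension ahead of Normal. One workable order is Crisis, Stage 2, Stage 1, Hypotension, Elevated, Normal. This also moves readings such as 125/55 from Elevated to Hypotension; swapping only the last two categories would leave them in Elevated. Under either order, readings with SBP ≥130 or DBP ≥80 stay hypertensive, so the row still will not hold every reading that meets the definition. A table footnote should say so.
- Write the bands as continuous ranges: SBP 120 to <130 and 130 to <140, DBP 80 to <90.

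The cost is one line, three band limits and a reordered program step. No data collection changes.

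Separately, section 9.5.4 of the Part 1 SAP has the same overlapping table and no priority rule. The problem there is ambiguity, not this misordering, and one sentence giving the same order would settle it. The protocol reports that Cohorts 1-6 are complete with preliminary top-line data available, so that addition should be documented as made after data were seen if that is the case.
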